8.4. Multiplicity

The primary and secondary efficacy hypotheses are to be tested in a hierarchy approach that specifies the order in which they are to be evaluated. This strategy requires that only when the primary endpoint meets significance will the secondary endpoint be tested. The order of testing will be: first, independent sitting (primary endpoint); second, event -free survival (secondary endpoint). Such pre-specification of the order of testing within hierarchical framework strongly prevents type 1 error inflation due to multiplicity.

9. ANALYSIS OF PHARMACOKINETICS

Not applicable to this SAP.

10. SAFETY

10.1. Extent of Exposure

The actual, weight-adjusted dose, in vg/kg, of AVXS-101 administered during the infusion will be summarized, as well as duration of infusion, whether the entire volume was delivered, and whether the infusion was interrupted.

10.2. Treatment Compliance

Weight-adjusted dose, in vg/kg, of AVXS-101 administered and dosing compliance of AVXS-101 will be summarized.

The treatment compliance of each patient at Baseline will be calculated as:

$$\text{Percentage of compliance (\%)} = 100\% * \text{total volume administered} / \text{planned dose}$$

The treatment compliance will be summarized by actual product received.

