10.2. Trial Product Dose and Dose Justification

Patients will receive a 1-time dose of AVXS-101 at 1.1×10^{14} vg/kg, equivalent to the dose received by Cohort 2 in the Phase 1 study via IV infusion administered in the completed Phase 1 clinical study (AVXS-101-CL-101).

Two doses were studied in the completed Phase 1 clinical study (AVXS-101-CL-101); the higher dose (dose received by the Cohort 2 patients) was chosen for the present study as preliminary data demonstrated both a dose response and significant clinical benefit thus identifying it as the proposed therapeutic dose. In the Phase 1 study, AVXS-101 demonstrated a dose response, with efficacy greater as observed by motor milestone achievement and CHOP INTEND scores at the higher dose (received by Cohort 2) than at the lower dose (received by Cohort 1). Direct testing of the actual lot of Investigational Medicinal Product (IMP) used in the AVXS-101-CL-101 study by an improved and more fully qualified analytical method has assigned a value of 1.1×10^{14} vg/kg to the actual dose received by Cohort 2 in this Phase 1 study. The same method has been used to establish an equivalent dose for the Phase 3 IMP. This vg/kg value has been further verified in an improved and more fully qualified SMN Δ 7 Mouse Biopotency assay to support a similar extension of mouse lifetime in direct comparative assessment between the Phase 1 and Phase 3 IMP.

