1.2. Glossary of Definitions

Abbreviations list pertains to the SAP only.

| Abbreviation | Description |
|-----------------|--|
| AE | Adverse Event: Any untoward medical occurrence in a clinical investigation subject which does not necessarily have a causal relationship with the drug or device under study. |
| Age | For a given event, age will be expressed in months and rounded to one decimal place. A month is standardized to a period of 30 days. Age at Event = (Date of Event – Date of Birth + 1)/ 30. Age at Dosing = (Date of Gene Therapy Infusion – Date of Birth + 1)/ 30. |
| Baseline | Baseline, e.g., in terms of baseline laboratory values, vital signs, or physical exam results, refers to a measurement or evaluation made prior to initiation of gene therapy infusion. If there are multiple measurements prior to the initiation of gene therapy infusion, only the latest measurement will be considered as baseline for analysis purposes. |
| BiPAP | Bilevel Positive Airway Pressure, a form of non-invasive mechanical pressure support ventilation. |

| Abbreviation | Description |
|------------------------------|---|
| CHOP-INTEND | Children’s Hospital of Philadelphia Infant Test of Neuromuscular Disorders, a 16-item motor function assessment validated for use in infants with spinal muscular atrophy. |
| Day 1 | The day of the gene therapy treatment. |
| Dose | Total vector genome administrated (in vg /patient weight on Day – 1(kg)). |
| MedDRA | Medical Dictionary for Regulatory Activities is a medical terminology used to classify adverse event information associated with the use of biopharmaceuticals and other medical products. |
| CTCAE | Common Terminology Criteria for Adverse Events version 4.03. The CTCAE is descriptive terminology, involving a severity scale, which is used for AE reporting in particular for unique patient populations. It is a subset of MedDRA terminology. |
| Permanent Ventilation | Requirement of ≥ 16 -hour respiratory assistance per day (includes BiPAP) continuously for ≥ 14 days in the absence of an acute reversible illness, excluding perioperative ventilation. |
| PNCR | Pediatric Neuromuscular Clinical Research Network |
| Study Day | For any event of interest, Study Day = calendar date of event – calendar date of gene transfer +1. Day 1 is the Study Day of the gene transfer and any events occurring on the same calendar day as the gene transfer. |

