7.4.1. Specific Medication Subgroups

To reduce the host immune response to the AAV-based therapy, patients will receive prophylactic prednisolone (approximately 1 mg/kg/day) 24 hours prior to the gene transfer and continuing for approximately 30 days. After 30 days of treatment, the dose of prednisolone can be tapered for patients whose ALT values, AST values, and T-cell response are ≤ 2 X ULN for ALT and AST, and < 100 SFC/ 10^6 PBMCs in accordance with the following treatment guideline:

- Weeks 5 and 6: 0.5 mg/kg/day
- Weeks 7 and 8: 0.25 mg/kg/day
- Week 9: prednisolone discontinued

The total number of days receiving prophylactic prednisolone and total cumulative dose of prophylactic prednisolone administered during the study (mg/kg, derived from the prednisolone log) will be computed for each patient. In case when other glucocorticosteroids were used, the doses should be converted into Prednisolone doses according to the conversion ratio, for example 4:1 for Hydrocortisone.

To compute total cumulative dose, the total dosing period is subdivided into dosing intervals represented by constant dose levels. On the day of a dosage change, the entire day is represented under the new dosing interval at the new dose.

For example, consider a patient who receives 1.0 mg/kg of prednisolone for Day 1 to Day 20, then on Day 20, dose is elevated to 2.0 mg/kg until Day 30, at which point it is tapered to 1.5 mg/kg. On Day 35, the dose is lowered to 1.0 mg/kg and continues until Day 40 when it is lowered further to 0.5 mg/kg until all prednisolone dosing stops on Day 45. For this patient,

$$\begin{aligned} \text{Total Cumulative Dose} &= (1.0 \text{ mg/kg} \times 19 \text{ days}) + \\ &\quad (2.0 \text{ mg/kg} \times 10 \text{ days}) + \\ &\quad (1.5 \text{ mg/kg} \times 5 \text{ days}) + \\ &\quad (1.0 \text{ mg/kg} \times 5 \text{ days}) + \\ &\quad (0.5 \text{ mg/kg} \times 6 \text{ days}) \\ &= 54.5 \text{ mg/kg} \end{aligned}$$

Exposure will be summarized for the Safety Analysis Set.

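### SAP 10.2 defines infusion compliance as a volume divided by a vg/kg dose, so it cannot give a percentage; SAP 7.4.1 leaves the prednisolone stop day undefined

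*SAP*

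**What the plan says.** **Compliance.** SAP 10.2 opens with "Weight-adjusted dose, in vg/kg, of AVXS-101 administered and dosing compliance of AVXS-101 will be summarized". It continues "The treatment compliance of each patient at Baseline will be calculated as", followed by a formula: 100% times "total volume administered" over the planned dose. The entry for Dose in the SAP glossary (1.2) begins "Total vector genome administrated (in vg /patient weight on Day" and goes on to Day -1 with weight in kg, so dose is in vg/kg. Protocol 10.2 uses the same unit: "Patients will receive a 1-time dose of AVXS-101 at" 1.1 × 10^14 vg/kg. SAP 10.1, directly above, plans summaries of the actual vg/kg given, the infusion duration, whether all of the volume went in, and whether the infusion was interrupted.

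**Prednisolone.** SAP 7.4.1 plans two per-patient quantities: the number of days on prophylactic prednisolone and the cumulative dose in mg/kg. Its counting rule is: "On the day of a dosage change, the entire day is represented under the new dosing interval at the new dose". A worked example then has five dose levels, the last running from Day 40 "until all prednisolone dosing stops on Day 45". It counts 19, 10, 5, 5 and 6 days and totals 54.5 mg/kg.

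**The concern.** A compliance percentage needs numerator and denominator in the same unit. Here the numerator is a volume and the denominator, by the SAP's own definition, is vector genomes per kilogram. A programmer who follows the text gets a number that is not a percentage. One who sees the problem must choose a substitute that the SAP does not name.

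The prednisolone example is likely to serve as the programming template for both steroid-exposure outputs. If its last interval is counted on a different convention from the others, the treatment of the final day is left to whoever writes the code. What is at stake in both cases is the correctness and reproducibility of descriptive exposure tables.

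**Working it through.** **1. Units of the compliance formula**

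Inputs: volume administered V, in mL (SAP 10.2); planned dose D = 1.1 × 10^14 vg/kg (Protocol 10.2); unit of dose, vg/kg (SAP 1.2 and 10.2).

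- As written: 100 × V / D, in mL per (vg/kg).
- If planned dose is read as total vg for an infant of weight w: 100 × V / (D × w), in mL per vg.
- Neither is dimensionless.

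The documents give no infusion volume or infant weight. To show the scale only, assume 20 to 60 mL:

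- 100 × 20 / (1.1 × 10^14) = 1.8 × 10^-11
- 100 × 60 / (1.1 × 10^14) = 5.5 × 10^-11

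On the total-vg reading, with an assumed weight of 3 to 8 kg, the range is 100 × 20 / (1.1 × 10^14 × 8) = 2.3 × 10^-12 to 100 × 60 / (1.1 × 10^14 × 3) = 1.8 × 10^-11. The mismatch does not depend on these assumptions.

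In like units, taking 40 mL as planned: full delivery gives 100 × 40/40 = 100%, and delivery of nine tenths gives 100 × 36/40 = 90%.

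The two natural repairs are volume over planned volume and total vg over planned total vg. If c is the vg-per-mL concentration, the second is (V × c) / (planned V × c), which reduces to the first. They agree only when the same c, and the same weight behind the planned amount, are used throughout.

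**2. The prednisolone example**

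The plan's figure reproduces: 1.0×19 + 2.0×10 + 1.5×5 + 1.0×5 + 0.5×6 = 19 + 20 + 7.5 + 5 + 3 = 54.5 mg/kg, over 19 + 10 + 5 + 5 + 6 = 45 days.

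Rebuilding the intervals from the narrative, with each change day at the new dose:

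| Dose (mg/kg) | Days by the rule | Count by the rule | Count in SAP |
|---|---|---|---|
| 1.0 | 1–19 | 19 | 19 |
| 2.0 | 20–29 | 10 | 10 |
| 1.5 | 30–34 | 5 | 5 |
| 1.0 | 35–39 | 5 | 5 |
| 0.5 | 40–44 or 40–45 | 5 or 6 | 6 |

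Four of the five intervals match. The fifth turns on whether Day 45 is a dosed day:

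- Day 45 dosed: 0.5 × 6 = 3.0, total 54.5 mg/kg over 45 days.
- Day 45 not dosed: 0.5 × 5 = 2.5, total 54.0 mg/kg over 44 days.
- Difference: 0.5 mg/kg, and 100 × 0.5 / 54.0 = 0.9%.

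The word *until* excludes the end day at Days 30 and 40 but must include it at Day 45 to give 6 days.

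**The case against.** **On compliance.** The fair reply is that this is a slip for planned volume, that any competent programmer would see it, and that a percentage near 10^-11 would never survive table review. That is probably true, and it is why a misleading published table is unlikely. It does not rescue the text. The SAP exists to fix derivations, this one cannot be carried out as printed, and the reader is not told which repair is meant.

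A reader might go further and infer that nothing else would show whether an infant received the full single dose. The documents do not support that. SAP 10.1 reports the vg/kg actually given, complete delivery of the volume, and interruption, so full delivery would be visible without the compliance percentage.

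**On prednisolone.** A reader might also infer that 54.5 mg/kg is a proven error and that every course would be overstated by a day. For that reading, the first four intervals exclude the end day, and the same section lists discontinuation at Week 9 as a step in the schedule, as if stopping were a change to zero. Against it, the rule concerns a change to a new dosing interval at a new dose, the intervals subdivide the dosing period, and stopping creates neither a new interval nor a new dose within that period. The five counts also add to exactly 45, which fits dosing on Days 1 to 45. The rule does not mention the stop date, so the documents do not settle the matter. What stands is an unstated convention and inconsistent wording.

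**Conclusion.** The compliance formula in SAP 10.2 is wrong as written: it mixes mL with vg/kg and cannot return a percentage. This rests only on the SAP's own definition of dose. The consequence is limited to one descriptive exposure summary, partly duplicated by SAP 10.1. The primary and secondary analyses, type I error and sample size are untouched.

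The prednisolone point is secondary and is an ambiguity. Either 54.5 mg/kg over 45 days or 54.0 mg/kg over 44 days can be right, depending on whether the recorded stop date is a dosed day. In the example the effect is one day at the final dose level. It carries through to both planned outputs, cumulative dose and days of exposure.

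**What to change.** - **SAP 10.2:** replace the formula with 100 × volume administered / planned volume, or 100 × total vg administered / planned total vg. Name one. If the vg version is chosen, state which concentration and which weight enter it. If planned volume is not in the database, say how it is derived.
- **SAP 7.4.1:** state whether the recorded prednisolone stop date counts as a dosed day, and make the example agree: 6 days and 54.5 mg/kg if it does, 5 days and 54.0 mg/kg if it does not. Apply the same convention to the count of days on prednisolone. This is a counting convention for the analysis and changes nothing in how patients are treated.

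The cost is about two lines of SAP text, best settled before the exposure tables are programmed. No new patient assessments are needed, and no other analysis is affected.

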10.3. Adverse Events / Adverse Drug Reactions

10.3.1. Treatment-Emergent Adverse Events

Adverse events will be coded using the Medical Dictionary for Regulatory Activities (MedDRA). Treatment-emergent adverse events are defined as any event that begins or worsens in severity after initiation of study drug through the last study visit. If an incomplete onset date was collected for an adverse event, the event will be assumed to be treatment-emergent, unless there is other evidence that confirms that the event was not treatment-emergent (e.g., the event end date was prior to the study drug start date).

10.3.2. Tabulations of Treatment-Emergent Adverse Events

Adverse event data will be summarized and presented using primary MedDRA system organ classes (SOCs) and preferred terms (PTs) according to the version of the MedDRA coding dictionary used for the study at the time of database lock. The actual version of the MedDRA coding dictionary used will be noted in the clinical study report. The system organ classes will be presented in alphabetical order and the preferred terms will be presented in alphabetical order within each system organ class.

Adverse events will be presented using Safety Set.

10.3.2.1. Adverse Event Overview

An overview of adverse events will be presented for each treatment group consisting of the number and percentage of patients experiencing at least one event for the following adverse event categories:

- Any treatment-emergent adverse event;
- Treatment-emergent adverse events with a "possibly related", "probably related", "definitely related" of being related to AVXS-101
 - Any AE reported as Possibly, Probably, or Definitely Related will be consolidated into a single category and summarized as "Related" in the tables

- Any AE reported as Unlikely Related or Unrelated will be consolidated into a single category and summarized as “Not Related” in the tables
- Grade 3 and 4 treatment-emergent adverse events;
- Serious treatment-emergent adverse events;
- Treatment-emergent adverse events leading to discontinuation of patient from study;
- Treatment-emergent adverse events leading to death;
- Deaths.

For the final analysis tables (i.e., after database lock of the study), just the two relatedness categories (“Related”, “Not Related”) will be presented.

For an interim run of this table (i.e., using an interim data cut), it is possible that there will be AEs with unknown relationship present. If this situation occurs, the table will present a third row (“Unknown”) in addition to “Related” and “Not Related” and the AEs with unknown relationship will be summarized in the “Unknown” row. If there are no AEs with unknown relationship in the interim cut of data, the “Unknown” row in the table will not be included.

Data listings, patient narratives, etc. will present the relationship to study treatment as collected on the CRF.

10.3.2.2. Adverse Event by SOC and PT

The following summaries of adverse events will be generated:

- Serious adverse events for screen failure patients only;
- Treatment-emergent adverse events;
- Treatment-emergent adverse events occurring in two (2) or more patients;
- Treatment-emergent adverse events categorized as "related" to AVXS-101;
- Serious treatment-emergent adverse events;
- Serious treatment-emergent adverse events related to AVXS-101;
- Grade 4 treatment-emergent adverse events;
- Grade 3 or 4 (see definition below) treatment-emergent adverse events;
- Treatment-emergent adverse events leading to discontinuation of patient from study;
- Treatment-emergent adverse events leading to death;
- Treatment-emergent adverse events leading to concomitant medication use (events with other action taken of "concomitant medication prescribed").
- Treatment-emergent adverse events of special interest (see section 10.3.2.4);

For all adverse event summaries, the number of treatment-emergent adverse events, the number and percentage of patients experiencing treatment-emergent adverse events will be tabulated according to SOC and PT. Patients reporting more than one adverse event for a given PT will be counted only once for that term (most severe incident for the severity tables and most related incident for the relationship tables). Patients reporting more than one adverse event within a

SOC will be counted only once for that SOC. Patients reporting more than one adverse event will be counted only once in the overall total.

A listing by treatment group of treatment-emergent adverse events grouped by body system and preferred term with patient numbers will be created.

10.3.2.3. Adverse Event by PT

The number of treatment-emergent adverse events and the number and percentage of patients experiencing treatment-emergent adverse events will be tabulated according to preferred term and sorted by overall frequency. Similar summaries will be provided for Grade 3 and 4 treatment-emergent adverse events and treatment-emergent adverse events with a "possibly related" to AVXS-101 categorization.

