13. ADVERSE AND SERIOUS ADVERSE EVENTS

13.1. Definition of Adverse Events

13.1.1. Adverse Event

An AE is the development of an undesirable medical condition or the deterioration of a pre-existing medical condition following or during exposure to a pharmaceutical product, whether or not considered casually related to the product. In clinical studies, an AE can include an undesirable medical condition occurring at any time, including baseline or washout periods, even if no trial treatment has been administered.

All AEs (related or not related) that occur after signing of the informed consent through the last trial visit will be collected and recorded in the eCRF.

All AEs will be classified in accordance with the CTCAE version 4.03 outlined in [Table 4](#).

Table 4: Common Terminology Criteria for Adverse Events

Grade	Definition
1	Mild; asymptomatic or mild symptoms; clinical or diagnostic observations only; intervention not indicated
2	Moderate; minimal, local or noninvasive intervention indicated; limiting age-appropriate instrumental ADL. ^a
3	Severe or medically significant, but not immediately life-threatening; hospitalization or prolongation of hospitalization indicated; disabling; limiting self-care ADL. ^b
4	Life-threatening consequences; urgent intervention indicated.
5	Death related to AE.

Source: Common Terminology Criteria for Adverse Events (version 4.03) [40]

^a Instrumental ADL refer to preparing meals, shopping for groceries or clothes, using the telephone, managing money, etc.

^b Self-care ADL refer to bathing, dressing and undressing, feeding self, using the toilet, taking medications, and not bedridden.

Additionally, a DSMB/DMC will review safety data on a quarterly basis. A detailed description of the DSMB/DMC, its role in this trial, and the timing and process of the scheduled reviews will be described in a DSMB/DMC Charter.

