13.2. Relationship to Trial Drug

An Investigator who is qualified in medicine must make the determination of relationship to the investigational product for each AE (Unrelated, Possibly Related, Probably Related, or Definitely Related). The Investigator should decide whether, in his or her medical judgment, there is a reasonable possibility that the event may have been caused by the investigational product. If no valid reason exists for suggesting a relationship, then the AE should be classified as “unrelated.” If there is any valid reason, even if undetermined, for suspecting a possible cause-and-effect relationship between the investigational product and the occurrence of the AE, then the AE should be considered “related.”

If the relationship between the AE/SAE and the investigational product is determined to be “possible” or “probable” then the event will be considered related to the investigational product for the purposes of expedited regulatory reporting.

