4.3. Safety Endpoints

Safety endpoint include physical examinations, pulmonary examinations, vital signs, capillary blood gas assessments, weight and length measurements, 12-lead ECGs, echocardiograms, 24-hour Holter monitors, swallowing tests, laboratory assessments, adverse event monitoring, and photographs of the infusion site. In general, safety assessments will be performed at the times scheduled in Table 1. All post-treatment visits are relative to the date on which gene replacement therapy is administered until the patient is 14 months of age, after which all visits will be relative to the patient’s date of birth.

The primary safety endpoint is the development of unacceptable toxicity, defined as the occurrence of any one Grade III or higher, unanticipated, treatment-related toxicity that presents with clinical symptoms and requires medical treatment

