6.2.4.4. Safety Variables

The safety endpoint is defined as the patient meeting the following criteria:

- Any AE
- Any serious AE
- Any AE related to study product
- Any AE with CTCAE Grade \geq Grade 3

This will be collected at all scheduled visits (see [Table 1](#)) from patient's CRF. Adverse Event collection methods for the observational natural history cohort were not consistent with rigorous Adverse Event collection methods demonstrated in the context of an interventional clinical research study; therefore, only descriptive statistics will be presented.

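### The severe-event summaries in SAP 10.3.2.1 to 10.3.2.3 stop at Grade 4, so no planned summary is specified to give the patient-level Grade 3-or-higher rate that the SAP names as a safety variable (minor)

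*SAP*

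**What the plan says.** Three SAP sections specify severe-event summaries:

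- The overview (10.3.2.1) has a row for "Grade 3 and 4 treatment-emergent adverse events".
- The list by system organ class and preferred term (10.3.2.2) has a Grade 4 table and a table of "Grade 3 or 4 (see definition below) treatment-emergent adverse events". No statement of what the Grade 3 or 4 band contains follows.
- The preferred-term section (10.3.2.3) says "Similar summaries will be provided for Grade 3 and 4 treatment-emergent adverse events and treatment-emergent adverse events with a" relatedness label, which ends "possibly related' to AVXS-101 categorization".

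Other text uses a wider band. Among the safety variables, SAP 6.2.4.4 lists "Any AE with CTCAE Grade" 3 or above. SAP 4.3 defines the primary safety endpoint through "the occurrence of any one Grade III or higher, unanticipated, treatment-related toxicity". Table 4 in Protocol 13.1.1 has five grades, and Grade 5 is "Death related to AE".

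For causality, Protocol 13.2 gives the investigator four levels: "Unrelated, Possibly Related, Probably Related, or Definitely Related". SAP 10.3.2.1 pools the last three as one related category for the tables.

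**The concern.** In a small single-arm trial in infants with a life-threatening disease, the proportion with a severe adverse event is a headline safety figure. A programmer who follows 10.3.2.1 to 10.3.2.3 literally would select Grades 3 and 4 and leave out Grade 5. The severe-event row would then not match the variable that the SAP names, and it would be lowered by the worst outcomes. In 10.3.2.3 a literal reading would also limit the relatedness table to the weakest of the three related levels.

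**Working it through.** The plan states no figure to reproduce. The check is a comparison of the sections, followed by simple arithmetic for scale.

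**1. Grade bands**

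| Place | Band | Includes Grade 5? |
|---|---|---|
| SAP 4.3, primary safety endpoint | III or higher | Yes |
| SAP 6.2.4.4, safety variable | 3 or above | Yes |
| SAP 10.3.2.1, overview | 3 and 4 | No |
| SAP 10.3.2.2, by class and preferred term | 4; 3 or 4 | No |
| SAP 10.3.2.3, by preferred term | 3 and 4 | No |
| SAP 10.3.2.5 and 10.3.2.6, maximum grade of each preferred term | No upper limit | Yes |

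**2. Where a fatal event is reported.** It is serious by definition (Protocol 13.1.2), so it enters the serious-event row of the overview and the serious-event table in 10.3.2.2. It also enters the leading-to-death summaries in both sections, the deaths row of the overview, and the maximum-grade tables.

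**3. Whether the Grade 3-or-higher patient rate can be recovered.**

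- The tables in 10.3.2.5 and 10.3.2.6 are specified by preferred term. One infant can appear under several terms, so adding the rows does not count infants.
- From the overview, let A be the number of infants with a Grade 3 or 4 event and D the number with a fatal event, taking fatal events as Grade 5. The number with Grade 3 or higher is A + D − B, where B is the number with both. The overview gives A and D but not B, so A + D counts B infants twice.
- If D = 1 and A is at least 1, the answer is A or A + 1. The overview cannot say which.

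**4. Size.** Protocol 7.2 plans 30 infants. Each infant whose only Grade 3-or-higher event was Grade 5 is missing from the overview row: 1/30 = 0.033, or 3.3 percentage points. An infant who also had a separate Grade 3 or 4 event is still counted, and the loss is zero.

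**5. Counting rule.** SAP 10.3.2.2 counts each infant once per preferred term, at the most severe incident in severity tables. Read literally, an infant whose worst grade under a term was 5 leaves that term's Grade 3 or 4 row, even with an earlier Grade 3 record. That is again 3.3 points for that term.

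**6. Relatedness.** SAP 10.3.2.1 pools three levels and 10.3.2.5 names all three. SAP 10.3.2.7 treats possibly related or higher as related when it resolves unknown relationships. Only 10.3.2.3 names a single level. The pooled related events are already tabulated by class and preferred term in 10.3.2.2.

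**The case against.** A reader might infer that fatal events, and events judged probably or definitely related, disappear from the safety report. The documents do not support that. Step 2 shows fatal events in several tables, including maximum-grade tables with no upper limit. Probably and definitely related events appear in the related-event table of 10.3.2.2, the maximum-grade table of 10.3.2.5 and the maximum-relationship table of 10.3.2.7. The pooling rule in 10.3.2.1 applies to the tables, and only two relatedness categories are to be shown in the final analysis. A possible-only table would contradict that rule, so the label in 10.3.2.3 is most plausibly shorthand.

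It can also be said that the definition promised in 10.3.2.2 does exist, because 10.3.2.6 explains that grades are adapted from CTCAE version 4.03. That covers how an event receives its grade. It does not say that a band written as 3 or 4 includes 5.

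Finally, 10.3.2.2 says that an infant with several events is counted once in the overall total. If the maximum-grade tables were programmed with an any-event row by highest grade, adding Grades 3, 4 and 5 in that row would give the missing rate. But 10.3.2.5 and 10.3.2.6 ask only for the maximum grade of each preferred term, so this depends on a choice that the SAP does not make.

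The objection therefore removes any claim of lost safety data. The mismatch between the severe-event rows and the SAP's own definition stands.

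**Conclusion.** The point holds as a minor inconsistency in named tables. The severe-event summaries in SAP 10.3.2.1, 10.3.2.2 and 10.3.2.3 use a narrower band than 4.3 and 6.2.4.4, and no planned summary is specified to give the patient-level incidence of any Grade 3-or-higher event. The effect is 3.3 percentage points per affected infant. This assumes 30 treated infants, literal programming of the band, and an infant with no separate Grade 3 or 4 event. It would be slightly smaller per infant if the sponsor approves enrolment beyond 30. The documents give no basis for predicting how many infants would be affected, and the number may be zero.

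The relatedness label in 10.3.2.3 is a drafting inconsistency. It affects one frequency-sorted table whose pooled counts are planned elsewhere.

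**What to change.** - In SAP 10.3.2.1, 10.3.2.2 and 10.3.2.3, replace the Grade 3 and 4 and Grade 3 or 4 wording with *Grade 3 or higher (3, 4 or 5)*, and delete the pointer to a definition below.
- Keep the separate leading-to-death and deaths rows, so that fatal events stay visible in their own right.
- In 10.3.2.3, replace the possibly related label with *related (possibly, probably or definitely)*.

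The cost is SAP wording, table titles and a selection condition in the programs. No new data or method is needed. The reported severe-event rate may rise slightly.
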